## **5.6 Withdrawal Criteria**

The study treatment must be withdrawn for any of the following reasons:

- 1) Overt disease progression
- 2) Intolerable AEs including the following:
  - Grade 4 non-hematological toxicity for which the relationship to the study drug is assessed as “related”
  - (For patients at Level 1) Grade 3 or higher QTcF prolongation or DLT
  - (For patients at Level 2) Any AE that does not lead to a situation allowing the resumption of study treatment, as specified in “5.5 Criteria for Temporary Discontinuation, Dose Reduction, and Resumption of Quizartinib.”
- 3) The need of the second dose reduction in patients with a dose reduction of the study drug
- 4) Achievement of CR, CRp, or CRi in Cycle 2 or later of consolidation therapy, leading to the decision of the investigator or subinvestigator to introduce HSCT
- 5) Patient’s withdrawal of consent for study participation
- 6) Ineligibility found after registration in the study
- 7) Patient found to be pregnant after registration in this study
- 8) Poor patient compliance with study procedures, including failure to visit the study center as scheduled in the protocol
- 9) Other circumstances why the study cannot be continued in the investigator’s or subinvestigator’s opinion

## **5.7 Prohibited Concomitant Drugs and Therapies, Restricted Concomitant Drugs, and Drugs to Be Coadministered with Care**

Prohibited concomitant drugs and therapies:

Concomitant use of the following drugs, etc. is prohibited during the quizartinib

treatment period.

As an exception, the drugs listed in 1) and 2) may be used only when the investigator or subinvestigator considers that these drugs are medically essential to prevent or treat infection. In this case, oral treatment with quizartinib should be interrupted from the start to the end of use of the drugs listed in 1) and 2), and be resumed on the following day of the end of use of the drugs. At the time of resumption, no dose reduction of quizartinib will be necessary unless the investigator or subinvestigator considers it necessary.

- 1) Drugs that may potentially prolong the QT/QTc interval
- 2) Strong CYP3A4 inhibitors
- 3) Strong or moderate CYP3A4 inducers
- 4) Crude drugs and food products with CYP3A4-inhibiting or -inducing properties (eg, foods and beverages containing St. John's wort or grapefruit)
- 5) Anticancer treatments other than quizartinib (except hydroxycarbamide)
- 6) Investigational drugs other than quizartinib, and investigational devices
- 7) Donor lymphocytes

Restricted concomitant drugs:

The following treatments should be restricted during oral treatment with quizartinib:

- Treatment with hydroxycarbamide for control of the white blood cell count:  
Restricted to a daily dose of 2 g for up to a total of 14 days

[Drugs to be coadministered with care]

During oral treatment with quizartinib, use of substrates and inhibitors of P-glycoprotein should be avoided as far as possible.

#### **<Rationale>**

These specifications are provided for proper safety evaluation of quizartinib.

Quizartinib and AC886 are mainly metabolized by CYP3A4. If the need arises to use drugs that may potentially prolong the QT/QTc interval or strong CYP3A4 inhibitors by necessity for the prevention or treatment of infection, concomitant use of these drugs with quizartinib should be avoided.

In addition, in vitro data indicate that quizartinib is a substrate of P-glycoprotein and that it inhibits P-glycoprotein. For this reason, concomitant use of quizartinib with substrates and inhibitors of P-glycoprotein should be avoided as far as possible.

Concomitant use of quizartinib with P-glycoprotein substrates may increase the blood concentrations of the P-glycoprotein substrates. Concomitant use of quizartinib with P-glycoprotein inhibitors may increase the blood concentration of quizartinib and AC886.

### **5.8 Symptomatic Therapy**

No specifications on symptomatic therapy are established in the study.

### **5.9 Management of Patients**

The investigator or subinvestigator will strive to ensure the maximum safety of patients throughout the study period. Patients must be hospitalized during the DLT assessment period (refer to “5.4.1 Definition of Dose-limiting Toxicities”). Patients will be allowed to make a temporary overnight stay outside the hospital during the hospitalization period if the investigator or subinvestigator considers it possible after careful examination of the patient. If a patient makes an overnight stay outside the hospital, the study staff at the study center will instruct the patient how to contact the study center in the event of an emergency, prior to making an overnight stay outside the hospital.

If an AE occurring during hospitalization does not resolve or is not relieved until the planned day of discharge, the investigator or subinvestigator will decide the need to continue hospitalization or not in consideration of patient safety assurance.

## **6. STUDY PROCEDURES**

Study procedures specified in the protocol are shown in “Table 6-1 and Table 6-2 Schedule of Study Procedures.”

In the study, the period from the day of informed consent through the end day of post-treatment observation is defined as the “study period” for each patient. However, if a patient has difficulty to attend the follow-up at the study center for reasons including transfer to another hospital or he/she refuses to visit the study center after the final dosing of quizartinib, then the study period for the patient will be terminated on the relevant day.

Table 6-1 Schedule of Study Procedures  
Remission Induction Therapy (Up to 2 Cycles)

	Day of Informed Consent	Day of Registration	Cycle 1									
			Day 1	Day 2	Day 3	Day 7	Day 8	Day 9	Day 11	Day 15	Day 21	Day 22
Informed consent	●											
Registration of patients		●										
Administration of the study drug and coadministered drugs*												
7 Quizartinib												
+ Cytarabine												
3 Daunorubicin or idarubicin			●	●	●							
5 Quizartinib												
+ Cytarabine												
2 Daunorubicin or idarubicin			●	●	●							
Baseline subject characteristics		●										
Medical history/complications		●										
Vital sign measurement**	● ≤ 7 days before registration	●a)				●b)	●	●c)	●b)	●	●e)	
Body weight	● ≤ 7 days before registration	●a)				●				●		●e)
ECOG PS assessment	● ≤ 7 days before registration	●a)				●				●		●e)
12-lead ECG**	● ≤ 14 days before registration	●a)				●b)	●	●c)	●b)	●	●e)	
Laboratory tests (hematology, blood chemistry, urinalysis)**	● ≤ 14 days before registration	●a)				●		●	●			●e)
Pregnancy test	○ ≤ 14 days before registration											
Assessment of bone marrow findings (antitumor effect)	● ≤ 14 days before registration									The day ●		
HIV antibody tests	● ≤ 14 days before registration											
Central measurement	Pharmacokinetics						●d)	●	●c)	●d)	●	●
	FLT3-ITD and c-KIT mutations		●a)									
	Phosphorylated protein levels in blood, including FLT3						●b)	●	●	●		
	Inhibitory activity of plasma quizartinib on phosphorylated FLT3 protein						●b)	●	●	●		
Assessment of concomitant drugs and therapies			←									
Monitoring of AEs			←									

Cycle 2												
		Day 1	Day 2	Day 3	Day 5	Day 6	Day 7	Day 8	Day 15	Day 19	Day 21	Day 28
Informed consent												
Registration of patients												
Administration of the study drug and coadministered drugs*												
7	Quizartinib											
+	Cytarabine											
3	Daunorubicin or idarubicin	●	●	●								
5	Quizartinib											
+	Cytarabine											
2	Daunorubicin or idarubicin	●	●									
Baseline subject characteristics												
Medical history/complications												
Vital sign measurement**		●a)!				5+2 ●c)	7+3 ●c)	●	5+2 ●	7+3 ●	●e)	
Body weight		●a)!									●e)	
ECOG PS assessment		●a)!				5+2 ●	7+3 ●		5+2 ●	7+3 ●	●e)	
12-lead ECG**		●a)!				5+2 ●c)	7+3 ●c)	●	5+2 ●	7+3 ●	●e)	
Laboratory tests (hematology, blood chemistry, urinalysis)**		●a)!				5+2 ●	7+3 ●	●	5+2 ●	7+3 ●	●e)	
Pregnancy test												
Assessment of bone marrow findings (antitumor effect)											The day ●	
HIV antibody tests												
Central measurement	Pharmacokinetics											
	FLT3-ITD and c-KIT mutations											
	Phosphorylated protein levels in blood, including FLT3											
	Inhibitory activity of plasma quizartinib on phosphorylated FLT3 protein											
Assessment of concomitant drugs and therapies												
Monitoring of AEs												

- Mandatory, ○ To be performed only in selected patients
- a) Before the start of administration of cytarabine and the anthracycline drug
- b) Pre-dose, 2 hours ( $\pm 10$  minutes) post-dose, 4 hours ( $\pm 10$  minutes) post-dose, and 6 hours ( $\pm 10$  minutes) post-dose
- c) Pre-dose, 2 hours ( $\pm 10$  minutes) post-dose, and 4 hours ( $\pm 10$  minutes) post-dose
- d) Pre-dose, 30 minutes ( $\pm 10$  minutes) post-dose, 1 hour ( $\pm 10$  minutes) post-dose, 2 hours ( $\pm 10$  minutes) post-dose, 4 hours ( $\pm 10$  minutes) post-dose, and 6 hours ( $\pm 10$  minutes) post-dose
- e) -3 days to the day

\* Remission induction therapy in Cycle 2 will be given using the same regimen as in Cycle 1 ("7 + 3") or on the dosing schedule ("5 + 2") shown in the table.

\*\*If drugs that may potentially prolong the QT/QTc interval or strong CYP3A4 inhibitors are used after the start of quizartinib treatment, quizartinib treatment should be interrupted from the start to the end of use of these drugs.

After the day when quizartinib is resumed, the following procedures will be performed at the time points listed below:

[1] Pre-dose of quizartinib on the day when the drug is resumed:	Vital sign measurement, 12-lead ECG, and laboratory tests
[2] 2 hours ( $\pm 10$ minutes) post-dose of quizartinib on the day when the drug is resumed:	Vital sign measurement and 12-lead ECG
[3] Pre-dose of quizartinib on Day 4 ( $\pm 1$ day) when defining the day when the drug is resumed as Day 1:	Vital sign measurement and 12-lead ECG
[4] Pre-dose of quizartinib on Day 8 ( $\pm 1$ day) when defining the day when the drug is resumed as Day 1:	Vital sign measurement and 12-lead ECG
[5] Pre-dose of quizartinib on Day 11 ( $\pm 1$ day) when defining the day when the drug is resumed as Day 1:	Vital sign measurement and 12-lead ECG
[6] Pre-dose of quizartinib on Day 15 ( $\pm 1$ day) when defining the day when the drug is resumed as Day 1:	Vital sign measurement and 12-lead ECG

! If Cycle 2 is started within +7 days reckoned from Day 28 of Cycle 1, the procedures scheduled on Day 1 of Cycle 2 are not necessary.

Table 6-2 Schedule of Study Procedures

	Before the Start of Treatment	Cycle 1								
		Day 1	Day 3	Day 5	Day 6	Day 7	Day 13	Day 19	Day 21	Day 28
Informed consent	●									
Registration of patients										
Administration of the study drug and coadministered drugs										
Quizartinib										
Cytarabine		●●	●●	●●						
Baseline subject characteristics										
Medical history/complications										
Vital sign measurement**		●a)			●b)		●c)	●		●d)
Body weight		●a)			●		●			●d)
ECOG PS assessment		●a)			●		●			●d)
12-lead ECG**		●a)			●b)		●c)	●		●d)
Laboratory tests (hematology, blood chemistry, urinalysis)**		●a)			●		●			●d)
Pregnancy test	◎ Within 7 days before treatment									
Assessment of bone marrow findings (antitumor effect)									The day ●	
HIV antibody tests										
Central measurement	Pharmacokinetics					●c)	●	●c)	●	●d)
	FLT3-ITD and c-KIT mutations									
	Phosphorylated protein levels in blood, including FLT3									
	Inhibitory activity of plasma quizartinib on phosphorylated FLT3 protein									
Assessment of concomitant drugs and therapies										
Monitoring of AEs										

Cycle 2 and Thereafter								At Withdrawal	Post-treatment Observation
	Day 1	Day 3	Day 5	Day 6	Day 13	Day 19	Day 21	Day 28	
Informed consent									
Registration of patients									
Administration of the study drug and coadministered drugs									
Quizartinib									
Cytarabine	••	••	••						
Baseline subject characteristics									
Medical history/complications									
Vital sign measurement**	●a) !			●	●	●	●d)	●e)	●f)
Body weight	●a) !						●d)	●e)	●f)
ECOG PS assessment	●a) !			●		●	●d)	●e)	●f)
12-lead ECG**	●a) !			●	●	●	●d)	●e)	●f)
Laboratory tests (hematology, blood chemistry, urinalysis)**	●a) !			●	●	●	●d)	●e)	●f)
Pregnancy test									
Assessment of bone marrow findings (antitumor effect)							The day ●		●e)
HIV antibody tests									
Central measurement	Pharmacokinetics								
	FLT3-ITD and c-KIT mutations								
	Phosphorylated protein levels in blood, including FLT3								
	Inhibitory activity of plasma quizartinib on phosphorylated FLT3 protein								
Assessment of concomitant drugs and therapies									
Monitoring of AEs									

- Mandatory, ○ To be performed only in selected patients
- a) Before the start of cytarabine administration
- b) Pre-dose, 2 hours ( $\pm 10$  minutes) post-dose, 4 hours ( $\pm 10$  minutes) post-dose, and 6 hours ( $\pm 10$  minutes) post-dose
- c) Pre-dose, 2 hours ( $\pm 10$  minutes) post-dose, and 4 hours ( $\pm 10$  minutes) post-dose
- d) -3 days to the day
- e) Day when study termination is decided (-3 days to +7 days)
- f) 28th day ( $\pm 7$  days) reckoned from the day of the last dose of the study drug

\*\*If drugs that may potentially prolong the QT/QTc interval or strong CYP3A4 inhibitors are used after the start of quizartinib treatment, quizartinib treatment should be interrupted from the start to the end of use of these drugs.

After the day when quizartinib is resumed, the following procedures will be performed at the time points listed below:

[1] Pre-dose of quizartinib on the day when the drug is resumed:	Vital sign measurement, 12-lead ECG, and laboratory tests
[2] 2 hours ( $\pm 10$ minutes) post-dose of quizartinib on the day when the drug is resumed:	Vital sign measurement and 12-lead ECG
[3] Pre-dose of quizartinib on Day 4 ( $\pm 1$ day) when defining the day when the drug is resumed as Day 1:	Vital sign measurement and 12-lead ECG
[4] Pre-dose of quizartinib on Day 8 ( $\pm 1$ day) when defining the day when the drug is resumed as Day 1:	Vital sign measurement and 12-lead ECG
[5] Pre-dose of quizartinib on Day 11 ( $\pm 1$ day) when defining the day when the drug is resumed as Day 1:	Vital sign measurement and 12-lead ECG
[6] Pre-dose of quizartinib on Day 15 ( $\pm 1$ day) when defining the day when the drug is resumed as Day 1:	Vital sign measurement and 12-lead ECG

! If the next cycle is started within +7 days reckoned from Day 28 of each cycle, the procedures scheduled on Day 1 of the next cycle are not necessary.

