Study 2689-CL-2004 was conducted in 76 FLT3-ITD positive AML patients, who were assigned to 28-day cycles of 30 or 60 mg/day continuous dosing of quizartinib (for both males and females) to evaluate the efficacy and safety of quizartinib at lower doses than those tested in Study AC220-002. In the study, the incidence of QTc prolongation was much lower than that observed in Study AC220-002, indicating that the risk of QTc prolongation was dose-dependent (Table 1.3-1). The study also demonstrated that the CRc rates were comparable to those observed in Study AC220-002 (Table 1.3-2). In Study 2689-CL-2004 as well, 34% of patients proceeded to HSCT, and the patients who underwent HSCT tended to have a longer survival than those who did not.

Common adverse events (AEs) reported in Studies AC220-002 and 2689-CL-2004 were gastrointestinal disorders (eg, nausea, diarrhea, and vomiting), hematotoxicities (eg, anemia, neutropenia, and thrombocytopenia), febrile neutropenia, fever, fatigue, and QTc prolongation. Although the hematologic toxicities appear to be associated with the underlying disease, AML, data suggest delayed recovery or continued suppression of absolute neutrophil count (ANC) and platelets as a consequence of continued treatment with quizartinib.

Table 1.3-1 Maximum Values of QT Corrected for Heart Rate Using Fridericia's Method (QTcF) and Maximum Changes from Baseline in QTcF in Two Phase 2 Studies

Daily Dose of Quizartinib	Study AC220-002			Study 2689-CL-2004	
	90 mg/day (N = 57) † Female	135 mg/day (N = 67) † Male	200 mg/day (N = 12)	30 mg/day (N = 38)	60 mg/day (N = 36)*
Maximum QTcF (ms)					
> 480, ≤ 500 (Grade 2)	21%	13%	33%	5%	14%
> 500 (Grade 3) † Asymptomatic	21%	15%	42%	5%	3%
Maximum change in QTcF from baseline (ms)					
≤ 30	9%	9%	0%	50%	44%
> 30, ≤ 60	46%	51%	8%	47%	36%
> 60	46%	39%	92%	3%	19%

\* Two patients in the 60 mg/day group were randomized but never treated with quizartinib.

Table 1.3-2 Composite Complete Remission and Partial Response Rates in Two Phase 2 Studies

Daily Dose of Quizartinib	Study AC220-002			Study 2689-CL-2004	
	90 mg/day (N = 57) † Female	135 mg/day (N = 67) † Male	200 mg/day (N = 12)	30 mg/day (N = 38)	60 mg/day (N = 38)
CRc rate	47%	45%	42%	47%	47%
PR rate	25%	28%	50%	13%	24%

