#### **6.5 Post-treatment Observation Period**

The procedures listed below will be performed at 28 days (±7 days) reckoned from the day of the last dose of the study drug. If any AE has not resolved at the time point when the procedures are performed, follow-up should be continued as far as possible until the AE is confirmed to have resolved or be resolving.

- Confirmation of survival or death (The “date of final confirmation” when the patient

is alive and the “date of death” when the patient is dead will be recorded in the CRF.)

- Vital sign measurement
- Body weight
- ECOG PS assessment
- 12-lead ECG
- Laboratory tests
- Monitoring of AEs
- Assessment of concomitant drugs and therapies (Concomitant drugs and therapies used for AEs, if any, will be recorded in the CRF.)
- Confirmation of the presence or absence of post treatment (If treatment meeting the definition specified in “6.6 Post Treatment” is started after the following day of the last dose of the study drug, the treatment regimen and the start date will be recorded in the CRF.)

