### **9.1 Definition of Adverse Events**

An AE is any untoward or unintended sign (including an abnormal change in laboratory findings or vital signs), symptom, or disease noted between the day of informed consent for the study and the end day of post-treatment observation, whether it is considered to be related to the study drug or not.

A symptom or disease preexisting before informed consent for the study is obtained will be handled as a complication, not as an AE. Any complication that is exacerbated after informed consent for the study is obtained should be handled as an AE, and the date when the exacerbation is detected will be recorded as the date of onset of the AE.

The progression of the underlying disease (AML) will be handled as described below:

- Tumor progression will not be handled as an AE, in principle. However, tumor progression leading to the outcome of death during the AE collection period should be handled as an SAE (with the name and outcome of the event recorded as “disease progression” and “fatal,” respectively).
- Tumor progression resulting in exacerbated signs or symptoms will be handled as an AE.

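### Ending the study period when a patient cannot or will not attend after the last quizartinib dose leaves no route to collect new adverse events and deaths up to day 28

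*Combined protocol and SAP*

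**What the plan says.** Section 6 defines each patient's study period as running from consent to the last day of post-treatment observation. It then makes an exception. The triggers are that "if a patient has difficulty to attend the follow-up at the study center for reasons including transfer to another hospital" or that "he/she refuses to visit the study center after the final dosing of quizartinib". The consequence is "then the study period for the patient will be terminated on the relevant day".

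Section 6.5 schedules one post-treatment assessment, at 28 days (±7) after the last dose. "Confirmation of survival or death" is an item of that assessment, as are the final adverse event check and the record of any later AML treatment. No remote contact is described for a patient who does not attend.

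Section 9.1 defines an adverse event as one "noted between the day of informed consent for the study and the end day of post-treatment observation". It does not say which day that is when the study period has been ended early.

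Three provisions partly offset the rule:
- Section 6.5 continues follow-up of events unresolved at the post-treatment assessment.
- Section 9.5.1 follows events that have occurred as far as possible, even beyond the end of the study, unless the patient is stable and safety is assured.
- Section 6.4 gives withdrawn patients an assessment with vital signs, ECG, laboratory tests, antitumor effect and adverse events, from 3 days before to 7 days after the decision.

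The Safety Analysis Set (Section 11.1.1) contains everyone who received any study or coadministered drug. The Section 3 rationale uses consolidation-phase safety data in deciding whether Japan can join the global Phase 3 study.

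**The concern.** The rule treats being unable or unwilling to come to the site as the end of all new data. Several items due at day 28 need no site visit: new adverse events, serious events, vital status and later AML treatment.

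Safety is a primary endpoint and is reported as frequency tables over all treated patients. A patient who leaves early still counts in the denominator as though observed to day 28, and any new event after leaving is absent from the numerator. The risks listed in Section 1.4, including delayed neutrophil and platelet recovery, infection and hemorrhage, can appear in the weeks after dosing. A death from disease progression is a serious event under Section 9.1 only if it falls within the adverse event collection period, so where that period ends decides whether such a death is reported at all.

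**Working it through.** The plan gives no figure for this point, so nothing has to be reproduced beyond the sample size: 2 levels × 3 = 6 and 2 levels × 6 = 12, which matches Section 11.5.

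**1. Where collection ends.** The study period in Section 6 and the adverse event window in Section 9.1 have the same two end points: consent and the end of post-treatment observation. Section 6 moves the second one forward for these patients. Section 9.1 names no other end date for them. The natural reading is that the window closes with the study period. On any other reading the window has no defined end. Either way the sections need reconciling.

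**2. What the offsetting provisions cover.**

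| Provision | Events already under way | New events up to day 28 | Vital status at day 28 |
|---|---|---|---|
| 6.5 and 9.5.1, continued follow-up | Yes, as far as possible | No | No |
| 6.4, withdrawal assessment | Yes | Only to the date of that assessment | No |
| 6.5, day 28 (±7) visit | Yes | Yes, if attended | Yes, if attended |

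A patient who completes treatment and then transfers is not a withdrawal, so Section 6.4 does not apply. On schedule, that patient's last dose is Day 19 of the consolidation cycle and the end-of-cycle visit is on Days 25 to 28, which is 6 to 9 days after the dose. If the patient leaves after that visit, 28 − 9 = 19 to 28 − 6 = 22 of the 28 days are uncovered (68% to 79%).

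**3. Follow-up lost.** For leaving on day t after the last dose, the share lost is (28 − t)/28:
- t = 0: 28/28 = 100%
- t = 7: 21/28 = 75% (14/21 = 67% to 28/35 = 80% over the visit window)
- t = 14: 14/28 = 50%

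With the half-life of about 3 days in Section 1.3.4, drug remaining is 0.5^(t/3): about 20% at day 7, 4% at day 14 and 0.2% at day 28. For effects driven by drug level, the first two weeks matter most.

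**4. Direction and possible size of the bias.** Let k of N patients leave, with late-event risk a in leavers and b in the others. Suppose the leavers go before any late event and none of their late events is captured. Then:
- true frequency = [k·a + (N − k)·b]/N
- expected observed frequency = (N − k)·b/N
- shortfall = k·a/N, which is never negative

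The documents give neither k nor the risks, so these values are assumptions chosen to show a range:

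| N | k | a | b | True | Observed |
|---|---|---|---|---|---|
| 12 | 1 | 10% | 10% | 10.0% | 9.2% |
| 6 | 1 | 10% | 10% | 10.0% | 8.3% |
| 6 | 1 | 20% | 10% | 11.7% | 8.3% |
| 6 | 1 | 40% | 10% | 15.0% | 8.3% |
| 12 | 3 | 40% | 10% | 17.5% | 7.5% |

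**5. Chance of seeing a late event at all.** With a 10% risk in every patient, 1 − 0.9^n gives 0.469 with 6 followed and 0.410 with 5; with 12 and 11 it gives 0.718 and 0.686.

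**The case against.** The strongest reply is that the plan does not simply stop looking. An infection, hemorrhage or cytopenia present at transfer must still be followed, including to a fatal outcome. Withdrawal for transplant or for progression triggers a full exit assessment. That Section 9.1 closes with the study period is inferred, not written. All of this stands, and it confines the gap to events that begin after the last contact, to vital status at day 28 and to later treatment.

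Four stronger readings are tempting, and the documents do not support them.
- **Selective loss.** A reader might infer that the rule removes the patients who go to transplant or who deteriorate. Section 6 names only "for reasons including transfer to another hospital or he/she refuses to visit the study center after the final dosing of quizartinib". Transplant is a withdrawal reason in Section 5.6 ("leading to the decision of the investigator or subinvestigator to introduce HSCT"), but a patient transplanted at the same center keeps the day 28 visit. A link between leaving and outcome is plausible but not established.
- **A count of affected patients.** A reader might start from "34% of patients proceeded to HSCT" in Section 1.3.2. That study enrolled FLT3-ITD positive patients on quizartinib without chemotherapy, and nothing says how many transplants involve a change of hospital.
- **Damage to the DLT decision.** Section 5.9 keeps patients in hospital during the DLT period, and withdrawal for transplant applies only from consolidation Cycle 2, after that period has closed. What remains is a patient whose last dose falls in induction and who leaves before consolidation; Section 5.4.4 already provides for discussing a replacement.
- **A biased survival result.** No survival endpoint or analysis is planned. Missing vital status matters only through unreported fatal events.

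It is also fair to say that remote contact will not recover QTcF or blood counts.

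**Conclusion.** The point holds in a limited form. For patients who transfer or refuse visits after the last dose, Section 6 read with Sections 6.5 and 9.1 leaves no route to new adverse events, serious events, deaths or later AML treatment up to day 28 (±7). Because they remain in the Safety Analysis Set denominator, a missed event can lower a reported frequency or leave it unchanged, but cannot raise it. The shortfall is larger if leaving is related to outcome. This bears on the adverse event tables and on the consolidation-phase data used for the Phase 3 participation decision.

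The size is unknown. The follow-up lost per patient is arithmetic: 75% for departure on day 7. The frequencies in the second table are illustrations on assumed risks. The conclusion also rests on reading the Section 9.1 window as closing with the study period, and on Section 11 as it stands: details are deferred to a Statistical Analysis Plan. An analysis rule there could change how shortened follow-up is reported, but it could not supply data that were never collected.

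**What to change.** 1. In Section 6, replace the automatic termination. Unless the patient withdraws consent to data collection, the study period runs to day 28 (±7) after the last dose for everyone. State that refusing visits is not in itself withdrawal of consent.
2. In Section 9.1, give the adverse event window the same end, so that it agrees with Sections 6, 6.5 and 9.5.1.
3. In Section 6.5, for patients who cannot or will not attend, waive only the on-site tests. Obtain new adverse events, serious events, vital status with its date, and later AML treatment by telephone or, with the patient's approval, from the receiving physician. Section 4.1.3.2 already foresees contact with other treating physicians on that condition.
4. Report the number of patients with shortened or remote follow-up beside the safety tables, with dates and reasons.

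The cost is a few sentences in three sections, possibly a line in the consent form, and about one contact per affected patient. Sample size and treatment do not change. Remote adverse event information will be less detailed, and ECG and laboratory data after departure will stay missing unless the receiving hospital supplies them.
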